## Document History

Version	Date	Change(s)	Author
Final Version 1.0	02NOV2023	Initial final version	[name]

## List of Abbreviations

Abbreviation	Definition
AE	adverse event
eCRF	electronic case report form
CSR	clinical study report
DSMC	data safety monitoring committee
IIH	idiopathic intracranial hypertension
MedDRA	medical dictionary for regulatory activities
PT	preferred term
SAE	serious adverse event
SAF	Safety population
SAP	statistical analysis plan
SC	subcutaneous
SD	standard deviation
SOC	system organ class
TEAE	treatment-emergent adverse event

## 1. Overview

This statistical analysis plan (SAP) describes the planned abbreviated analysis and reporting for Invex Therapeutics protocol number INVEX-CLIN-IIH-301 (A Phase III randomised, placebo-controlled, double-blind, multi-centre, clinical trial to determine the efficacy and safety of Presendin™ in idiopathic intracranial hypertension), protocol version 4.0, dated 09JUL2022, and protocol version 5.0 (countries of the European Union), dated 08DEC2022.

The study was early terminated due to commercial reasons in Aug 2023, with only a very small number of patients enrolled. All patients finally consented were in countries working with protocol version 4.0.

This analysis plan only covers the analysis that is finally planned to be conducted for this early terminated study.

The statistical plan described hereafter is an *a priori* plan. It will be approved before any unblinded inferential or descriptive analysis of data pertaining to Invex Therapeutics's study INVEX-CLIN-IIH-301.

## 2. Study Objectives and Endpoints

Original study objectives and endpoints are listed in protocol section 2. It was decided to restrict the planned analysis to the most relevant safety endpoints only (adverse events and safety laboratory data).

## 3. Overall Study Design and Plan

### 3.1. Overall Design

This is a randomised, placebo-controlled, double-blind, multi-centre clinical trial, initially planned in approximately 240 randomised patients with idiopathic intracranial hypertension (IIH).

The trial is designed as follows:

The trial begins with a 1-week screening period. The screening period is followed by a 24-week randomised double-blind treatment period in which patients will be randomised (1:1) to receive a subcutaneous (SC) dose of either Presendin containing 2mg of exenatide (active group) or matching placebo (placebo group), self-administered once weekly. At the end of the randomised treatment period (Week 24), all patients have an end of treatment clinic visit. Five weeks after the end of that treatment visit, an end of trial safety follow-up telephone visit is performed. For full details of the study design, please see the protocol.

### 3.2. Study Population

Patients with a diagnosis of IIH according to the protocol and meeting the eligibility criteria.

### **3.3. Treatments Administered**

There are two treatment groups with patients randomised in a ratio of 1:1 to receive active treatment (Presendin) or placebo.

### **3.4. Schedule of Events**

Please see protocol Table 1 for a detailed schedule of study assessments.

## **4. Statistical Analysis and Reporting**

The final statistical analysis will be performed after the clinical study database is locked and the study is unblinded. A synoptic clinical study report (CSR) summarizing all planned analyses according to this analysis plan will be prepared. Other analyses as part of the protocol are finally not planned to be performed by statistics due to the early study termination. In addition, the medical writer may review relevant raw data and relevant conclusions based on raw data may be included in the CSR.

### **4.1. Introduction**

Data processing and tabulation of descriptive statistics will primarily use SAS (release 9.4 or higher). If the use of other software is warranted, the final statistical methodology report will detail what software was used for what purposes.

Continuous (quantitative) variable summaries will include the number of patients (n) with non-missing values, mean, standard deviation (SD), median, minimum, and maximum.

Categorical (qualitative) variable summaries will include the frequency and percentage of patients who are in the particular category or each possible value. In general, the denominator for the percentage calculation will be based upon the total number of patients in the relevant analysis population for the treatment groups, unless otherwise specified. The denominator for by-visit displays will be the number of patients in the relevant analysis population with non-missing data at each visit.

The minimum and maximum will be reported with the same degree of precision (i.e., the same number of decimal places) as the observed data. Measures of location (mean and median) will be reported to 1 degree of precision more than the observed data and measures of spread (SD) will be reported to 2 degrees of precision more than the observed data.

Percentages will be presented to 1 decimal place, unless otherwise specified.

Due to the early study termination all statistical analyses performed will be descriptive.

### **4.2. Interim Analysis and Data Monitoring**

A Data Safety Monitoring Committee (DSMC) was planned to be established for this study.

Finally due to early study termination, no DSMC meeting other than the DSMC kick-off meeting took place; thus, no unblinded data were presented to the DSMC.

Also, no other formal interim analyses were planned or conducted.

## 5. Analysis Populations

Due to the early termination of the study, all tables and listings (except disposition information) are planned to be presented for the Safety population. No other analysis populations will be implemented.

**Safety Population (SAF):** The Safety population includes all patients randomised to treatment (active or placebo) who received at least one dose of study medication.

Due to the limited number of patients, it is likely that the unblinded randomized treatment will match the actual treatment in all cases. This will be re-checked based on the unblinded data. If there are no discrepancies, a footnote will be added to the output to indicate that actual and randomized treatment are the same for all patients. If any discrepancies occur between randomized and actual treatment, the actual treatment will be used for all tables/listings. Any patient who received Presendin at least once will be included under Presendin treatment for all tables/listings. In this case, the information about the randomized treatment will be added to the disposition listing.

## 6. General Issues for Statistical Analysis

### 6.1. Statistical Definitions and Algorithms

#### 6.1.1. Baseline

There is no specific baseline definition. Tables by visit will contain “Screening (Visit 1) – Week – 1” as well as “Baseline (Visit 2) – Week 0 (Day 1)” reported separately. Changes from baseline will not be calculated.

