## **8.5. Clinical Laboratory Evaluations**

Laboratory test results for each biochemistry (including glucose) and haematology parameters (including coagulation) will be summarized descriptively by treatment group and timepoint as observed values.

The number of patients with clinical laboratory (biochemistry and haematology) values categorized as below, within, or above the normal ranges will be tabulated in a frequency table for each clinical laboratory analyte by treatment group and timepoint.

Abnormal laboratory values will be displayed in the data listings, along with corresponding normal ranges.

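### The planned laboratory outputs do not link a patient's pre-dose and post-dose values, so a new abnormality often cannot be told from a pre-existing one

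*SAP*

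**What the plan says.** SAP section 2 restricts the analysis to adverse events and safety laboratory data. On baseline, section 6.1.1 says "There is no specific baseline definition". The Screening visit (Visit 1) and the Baseline visit (Visit 2, Day 1) are to appear in by-visit tables as two separate timepoints, and the section ends by stating that "Changes from baseline will not be calculated".

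Section 8.5 plans three laboratory outputs:
- Results "will be summarized descriptively by treatment group and timepoint as observed values".
- Counts of patients with "values categorized as below, within, or above the normal ranges will be tabulated in a frequency table", again by treatment group and timepoint.
- A listing: "Abnormal laboratory values will be displayed in the data listings, along with corresponding normal ranges".

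Section 4.1 sets the by-visit denominator as the patients with non-missing data at that visit and makes all analyses descriptive. Section 1 records early termination with very few patients enrolled and does not give the number.

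**The concern.** The usual question for laboratory safety data is whether a patient's value moved after dosing. That needs a reference value for the same patient. The SAP has pre-treatment values and shows them, but treats them only as further timepoints in group summaries. A patient who was out of range throughout and a patient who went out of range on treatment each add one to the same post-dose cell.

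Adverse events are handled differently. Section 8.1 defines treatment emergence by first onset or worsening after the first dose and gives detailed rules for incomplete dates. Section 8.5 has no counterpart for laboratory values. At stake is whether the synoptic report can say, from planned output, which laboratory abnormalities arose after dosing.

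**Working it through.** The SAP gives no figure to reproduce here. The check asks how much the planned outputs reveal about new abnormalities.

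**1. Per-visit counts.** Take n patients in an arm with complete data, *a* of them abnormal before dosing and *b* abnormal at a post-dose visit. For simplicity, abnormal is treated as one category. The number newly abnormal must lie between

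max(0, b − a) and min(b, n − a).

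The SAP does not give n, so the values below are assumptions.

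| n | a | b | Lower limit | Upper limit | New abnormalities |
|---|---|---|---|---|---|
| 5 | 0 | 2 | max(0, 2) = 2 | min(2, 5) = 2 | exactly 2 |
| 5 | 1 | 2 | max(0, 1) = 1 | min(2, 4) = 2 | 1 to 2 |
| 5 | 2 | 2 | max(0, 0) = 0 | min(2, 3) = 2 | 0 to 2 |
| 10 | 3 | 3 | max(0, 0) = 0 | min(3, 7) = 3 | 0 to 3 |

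The two limits coincide only when *a* or *b* equals 0 or n. Of the (n + 1)² possible count pairs, (n − 1)² therefore leave the number of new cases open:
- n = 3: 4 of 16
- n = 5: 16 of 36
- n = 10: 81 of 121

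These are shares of possible tables, not probabilities, because the pairs are not equally likely. They show that the ambiguity is common but not universal.

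**2. Changing denominators.** Under section 4.1, the patients summarised can differ from visit to visit, so the difference between two visit means need not be the mean of any patient's change. Missing values also weaken the clear case in the first row. Suppose only 4 of 5 patients have a Visit 2 value, none of them abnormal, and 2 of 5 are abnormal post-dose. The patient without a Visit 2 value may be one of those 2. The counts then show only that at least 2 − 1 = 1 abnormality is new relative to Visit 2.

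**3. The listing.** As described, it holds abnormal values only. A patient abnormal before and after dosing can be recognised. For a patient with only a post-dose entry, the pre-dose value may have been normal or may be missing, and the listing does not say which. Movement within the normal range does not appear at all.

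**4. The reference value.** The SAP does not say that Visit 2 laboratory samples are taken before the first dose. Without a baseline definition, a reader of the tables does not know whether Visit 1 or Visit 2 is the pre-dose reference.

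**The case against.** The strongest reply is that this is an openly stated choice. The trial stopped for commercial reasons, the SAP declares an abbreviated analysis (sections 1, 2 and 9), and sections 6.1.1 and 8.5 agree with each other. Pre-treatment values are shown by group at two visits. With very few patients, reading the listing of abnormal values is practical. Section 4 also lets the medical writer review raw data and draw conclusions from them in the report. The listing layouts are in a separate document (section 11.1) and may be fuller than section 8.5 suggests.

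Most of this stands, and it limits the severity. It does not remove the point. A shift table is also descriptive, and few patients make a within-patient display more useful than group summaries. The raw-data review is optional and has no stated content, so it does not replace a planned output. The shells cannot be judged here, but the SAP text commits only to abnormal values.

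Two stronger readings are tempting, and the document supports neither:
- A reader might infer that the trial has no baseline laboratory data, or that the outputs can never separate new from pre-existing abnormalities. The Screening and Baseline visits are displayed. If nobody is abnormal before dosing and data are complete, every later abnormality is new.
- A reader might infer that chance baseline differences would bias a comparison between arms. No inferential comparison is planned, and the SAP gives neither the number per arm nor a within-patient correlation from which to size such an effect. Mean change by arm would add little at this sample size.

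**Conclusion.** The point holds in a limited form. No planned laboratory output ties a patient's pre-dose value to the same patient's post-dose value. The counts often leave the number of new abnormalities open, and the abnormal-only listing closes that gap only in part. The conclusion about linkage rests on the text of sections 6.1.1 and 8.5 alone. The illustration of ambiguity assumes n of 3, 5 or 10 and complete data.

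The severity is low. The study is terminated, very small and descriptive, and no efficacy or inferential result depends on these tables. It is still worth correcting, because laboratory values are one of only two safety domains kept.

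**What to change.** - In section 6.1.1, replace the statement that there is no baseline definition with one for laboratory data: the last non-missing value before first dose.
- In section 8.5, add a shift table for each analyte by arm: low, normal or high at baseline against post-baseline. A missing category at baseline would keep missing apart from normal.
- At minimum, if no shift table is added, list all laboratory values, normal ones included, for any patient with a post-dose abnormality. In so small a study this closes most of the gap.
- Mean change by arm and visit is optional. If it is left out, the sentence ruling out change from baseline can stay.

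The cost is one derivation and a little extra programming on data already collected. The listing-only option is the cheapest.

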#### 6.1.2. Analysis Visits

In general, scheduled visits as reported in eCRF will be used for analysis. No visit windowing is planned.

## 7. Study Patients and Demographics

### 7.1. Disposition of Patients and Withdrawals

Disposition of patients will include tabulations of the number of screened patients, tabulated reasons for screen failure, number of patients randomised into each treatment group, the number of patients who received treatment, the number of patients completing 24-weeks of randomised treatment, the number of patients completing study, tabulated reasons for discontinuation from the

study, tabulated reasons for discontinuation of study medication (without withdrawal from study) and number of patients in the Safety population.

In addition, treatment and study completion status and reasons for study withdrawals will be listed.

## **7.2. Demographics and Other Baseline Characteristics**

Summary statistics for age, sex, race, and ethnicity will be presented by treatment group and overall.

All demographic and baseline characteristics will also be displayed in a data listing.

## **7.3. Exposure and Compliance**

Investigational product administration will be listed based on the exposure (study drug administration) page from the eCRF.

## **8. Safety and Tolerability Analysis**

Safety will be evaluated from reported adverse events (AEs) and clinical laboratory values.

All safety analyses will be performed on the Safety population.

### **8.1. Adverse Events**

All AEs, treatment-emergent adverse events (TEAEs), and serious adverse events (SAEs) will be coded using the Medical Dictionary for Regulatory Activities (MedDRA) dictionary (version 25.0 or later).

An AE is defined as treatment-emergent if the first onset or worsening is after the first administration of study medication.

If the start date and time of an AE are partially or completely missing, the AE will be assumed to be treatment-emergent if it cannot be definitely shown that the AE did not occur or worsen during the treatment-emergent period (worst-case approach).

For missing or partial AEs onset dates and times, the convention for replacing missing or partial dates will be the following based on the worst-case approach:

For partial AE start dates:

- If the year is unknown, then do not impute the date but assign a missing value. The AE will then be considered as a TEAE.
- If the month and day are unknown, then:
  - If the year matches the year of first treatment date, and the end date (if present) is after first treatment date, then impute as the month and day of the first treatment date.
  - Otherwise, assign 1st of January.

- If only the day is unknown, then:
  - If the month and year match the month and year of the first treatment date, then impute as the day of first treatment date.
  - If this produces a date after the AE end date, assign the start date to the 1st day of the month.
  - Otherwise, assign the 1st day of the month.

Missing or partial AE end dates will not be replaced.

If partial or missing times occur for AE at the day of first treatment, AE will be considered as TEAE, unless it cannot be definitely shown that the AE did not occur or worsen during the treatment-emergent period (worst-case approach).

An overall summary table of TEAEs will be produced.

The number and percentage of patients reporting TEAEs, grouped by MedDRA system organ class (SOC) and preferred term (PT), will be tabulated by treatment group. Summaries will be presented for all TEAEs and treatment-related TEAEs.

In the case of multiple occurrences of the same TEAE within the same patient, each patient will only be counted once for each PT.

If a particular event is missing the severity and/or relationship, then the strongest possible severity or relationship will be assumed for analysis (severity = Grade 4/life-threatening, relationship = probable relationship).

In the AE data listings, all AEs will be displayed. Adverse events that are treatment-emergent will be indicated as such.

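### Two of the partial-start-date rules in SAP section 8.1 do not match the SAP's own TEAE definition and worst-case approach for a few rare date patterns

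*SAP*

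**What the plan says.** SAP section 8.1 defines the term first: "An AE is defined as treatment-emergent if the first onset or worsening is after the first administration of study medication". For partial or missing onset it then sets a general principle: "the AE will be assumed to be treatment-emergent if it cannot be definitely shown that the AE did not occur or worsen" in the treatment-emergent period. It says that the replacement rules rest on this worst-case approach. The rules that matter here are:

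- **Year unknown:** "then do not impute the date but assign a missing value. The AE will then be considered as a TEAE". The end date is not consulted.
- **Month and day unknown:** the first treatment date is imputed under the condition "If the year matches the year of first treatment date, and the end date (if present) is after first treatment date". The fallback is "Otherwise, assign 1 st of January".
- **Day unknown:** in the month of first treatment, the first treatment day is imputed, with this check: "If this produces a date after the AE end date, assign the start date to the 1 st day of the month".
- **End dates:** "Missing or partial AE end dates will not be replaced".

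**The concern.** The rules claim to carry out the worst-case principle, so they can be tested against it. Two of them fail for particular patterns.

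The month-and-day rule needs an end date strictly later than first treatment. An AE that ended on the first treatment day could have begun and resolved after the dose on that day, yet it is dated to 1 January. The year-unknown rule errs the other way: it labels an AE treatment-emergent even when its end date shows that it was over before dosing.

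At stake is the TEAE flag. It feeds the overall TEAE summary, the tables of all and treatment-related TEAEs by SOC and PT (section 8.1), the table of TEAEs leading to withdrawal (section 8.2) and the marker in the AE listing. Adverse events and laboratory values are the only safety evaluations kept in the abbreviated analysis (sections 2 and 8).

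**Working it through.** The plan gives no figure to reproduce. The check applies each rule to concrete dates and compares the result with the worst-case principle.

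**Inputs.** The rules are those of SAP section 8.1. The SAP gives no first-dose date, so 15 March 2023 is assumed for illustration. An AE dated to Day 1 without a time is taken as a TEAE, which is the evident intent of the worst-case approach.

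**Month and day unknown, start recorded as 2023**

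| End date | Imputed start | Could onset be on Day 1 or later? | Agrees with principle? |
|---|---|---|---|
| missing | 15 Mar 2023 | yes | yes |
| 14 Mar 2023 | 1 Jan 2023 | no | yes |
| 15 Mar 2023 | 1 Jan 2023 | yes, on 15 Mar after the dose | **no** |
| 16 Mar 2023 | 15 Mar 2023 | yes | yes |
| Mar 2023 (day unknown) | not determined by the text | yes, 15 to 31 Mar | depends on reading |

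**Day unknown, start recorded as Mar 2023**

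- End 15 Mar: the imputed 15 Mar is not after the end date, so it stands. The AE is on Day 1.
- End 14 Mar: the imputed 15 Mar is after the end date, so the start becomes 1 Mar. The AE is pre-dose, which is right.

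The two rules therefore treat an AE ending on the first treatment day in opposite ways.

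**Partial end date.** With end Mar 2023, the test of being after 15 March cannot be evaluated, and the end date is not replaced. If it is treated as absent, the imputed start is 15 March. If the test is treated as failed, the imputed start is 1 January, and an AE that could have begun as late as 31 March becomes pre-dose. The SAP does not choose. Neither default suits every case: treating an end of Feb 2023 as absent would date to 15 March an AE that was plainly over before dosing.

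**Year unknown.** With end 10 Mar 2023, the AE ended before 15 March, so neither onset nor worsening can follow the first dose. The rule still makes it a TEAE.

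**Enumeration.** For four assumed first-dose dates, every complete end date from 1 Jan 2022 to 31 Dec 2024 (365 + 365 + 366 = 1,096 dates), and no end date, was tried with start years 2022 to 2024.

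| Assumed first dose | Patterns wrongly dated pre-dose | End dates before first dose, still TEAE if year unknown |
|---|---|---|
| 1 Jan 2023 | 0 | 365 |
| 20 Jan 2023 | 1 | 365 + 19 = 384 |
| 15 Mar 2023 | 1 | 365 + 31 + 28 + 14 = 438 |
| 31 Jul 2023 | 1 | 365 + 211 = 576 |

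The single pattern is always the same: month and day unknown, first-treatment year, end date equal to the first treatment date. The day-unknown rule gave no error in either direction. The last column counts calendar dates and says nothing about how often such records occur.

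**The case against.** **The imputed date may not set the flag.** The general sentence on TEAE status stands apart from the replacement rules, and only the year-unknown rule assigns a flag outright. On that view, an AE ending on Day 1 stays a TEAE whatever date is imputed. This is a fair reading, but the SAP does not say which text prevails, and a program driven by dates would follow the rules. If the general sentence prevails, the 1 January date still contradicts it.

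**Partial end dates.** A reader might infer that every AE with a partial end date is pushed to 1 January, so that AEs beginning well after Day 1 are lost. The text does not compel this. An end date that is not replaced can as naturally count as not present, which gives the first treatment date. What stands is an ambiguity.

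**Year unknown.** A reader might infer that this rule breaks the worst-case principle. It does not break it as worded: the principle says when to assume a TEAE and gives no explicit converse. The conflict is with the TEAE definition, and the error only over-counts. With a screening period of one week (section 3.1), such records should be rare.

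**Reach.** A reader might infer that every AE table is affected. The SAE table in section 8.3 is not limited to TEAEs, and the listings show all AEs.

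**Neighbouring sentence.** The sentence on missing times on Day 1 has an exception worded the reverse of the principle. Read literally, it could unflag AEs dated to Day 1 without a time. The working above reads it by intent.

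**Conclusion.** The point holds as a minor one. Two stated rules give a date or flag that conflicts with section 8.1 itself:

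1. The month-and-day rule dates a same-year AE ending on the first treatment day to 1 January. That is pre-dose unless dosing began on 1 January, and it is against both the worst-case approach and the day-unknown rule.
2. The year-unknown rule counts as a TEAE an AE that a complete end date shows was over before dosing.

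The treatment of a partial end date is unclear and needs a stated rule.

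With complete end dates, wrongful pre-dose dating is confined to one pattern, and whether any AE in the trial has it is unknown. One reclassified patient moves an arm's percentage by 100/n points, provided that the patient has no other TEAE counted in that row. The SAP does not give n and says only that very few patients were enrolled (section 1). For assumed arms of 5 and 10 this is 100/5 = 20 and 100/10 = 10 points. All analyses are descriptive (section 4.1), so no test result is affected.

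**What to change.** Change two rules in section 8.1:

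- **Month and day unknown, year of first treatment:** impute the first treatment date unless the known parts of the end date show that the AE ended before the first treatment date. Only then assign 1 January.
- **Year unknown:** do not impute. Consider the AE a TEAE unless the known parts of the end date show that it ended before the first treatment date.

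Referring to the known parts of the end date settles partial end dates without imputing them. With these changes the rules and the general sentence agree for the patterns above, so which of them prevails no longer matters there. The exception in the Day 1 missing-time sentence should be aligned with the principle in the same edit.

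The cost is two lines of SAP wording, the small alignment just mentioned and a short edit to the derivation program. No new data are needed.

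### The SAP's rule for missing adverse event times on the day of first treatment is the logical opposite of its general missing-date rule and of its own worst-case label, most likely through a slip of 'cannot' for 'can'

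*SAP*

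**What the plan says.** All the relevant text is in SAP section 8.1 (Adverse Events).

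- **Definition.** "An AE is defined as treatment-emergent if the first onset or worsening is after the first administration of study medication".
- **General rule.** For an onset date and time that are partly or wholly absent, the SAP rules as follows: "the AE will be assumed to be treatment-emergent if it cannot be definitely shown that the AE did not occur or worsen". The window it refers to is the treatment-emergent period, and the rule is labelled a worst-case approach.
- **Partial dates.** Where only the day is unknown: "If the month and year match the month and year of the first treatment date, then impute as the day of first treatment date". Where month and day are unknown, the year is that of first treatment and any end date is later than first treatment, "then impute as the month and day of the first treatment date". No time is imputed.
- **Missing times on the first day.** The sentence opens with its scope: "If partial or missing times occur for AE at the day of first treatment". For those records it then gives this outcome: "AE will be considered as TEAE, unless it cannot be definitely shown that the AE did not occur or worsen during the treatment-emergent period". This sentence is also labelled a worst-case approach.

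The flag drives an overall TEAE summary and the tables by system organ class and preferred term ("Summaries will be presented for all TEAEs and treatment-related TEAEs"). It also drives the table of TEAEs leading to withdrawal (section 8.2) and the treatment-emergent indicator in the adverse event listing (section 8.1).

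**The concern.** The two rules share one condition and attach opposite outcomes to it. In the general rule, being unable to rule out the treatment-emergent period makes the event a TEAE. In the first-day sentence, the same inability is what takes TEAE status away. Only the first is a worst-case approach.

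On the first treatment day the date alone cannot settle whether an event came before or after the dose, so the missing-time rule decides. It is also the day on which early drug or injection reactions would begin. Section 2 restricts the analysis to adverse events and safety laboratory data, so the TEAE tables are a main output. Section 1 describes the SAP as an a priori plan to be approved before any unblinded analysis. If the conflict stays in the text, a programmer and an independent checker could each follow a different sentence and both claim to have followed the plan. Choosing between them after unblinding would be a post hoc decision on which events count.

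**Working it through.** The plan gives no figure to reproduce. The check is one of logic.

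**Step 1: name the condition.** Let D mean that the event can definitely be shown not to have occurred or worsened in the treatment-emergent period. 'Cannot be shown' is then not-D. For an event on the first treatment day, not-D means the timing is undetermined, and D means it is shown to be pre-dose.

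**Step 2: write each rule in terms of D.**

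- General rule: TEAE if not-D.
- First-day rule as written: TEAE unless not-D, so not-D gives no TEAE and D gives TEAE.
- First-day rule with 'can' in place of 'cannot': TEAE unless D.

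**Step 3: compare the outcomes.**

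| State of the event | General rule | First-day rule as written | First-day rule with 'can' |
|---|---|---|---|
| Timing undetermined (not-D) | TEAE | not TEAE | TEAE |
| Shown to be pre-dose (D) | not TEAE | TEAE | not TEAE |

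The rule as written disagrees with the general rule in both rows, so it is its exact complement. In the second row it also conflicts with the definition, which requires onset or worsening after the first administration. With the one-word change the two rules agree in both rows.

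**Step 4: do both rules cover the same record?** Yes. The general rule covers missing start dates and times, so a first-day event with no usable time falls under it as well as under the first-day sentence. The SAP does not say which takes precedence.

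**Step 5: do imputed dates reach the sentence?** The two partial-date rules quoted above can place an event on the first treatment date without a time. If the sentence is then applied to the imputed record, that record is affected too. The SAP does not say whether it should be.

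**Step 6: possible size.** The SAP gives neither arm sizes nor a count of affected events; section 1 says only that very few patients were enrolled. As an assumption, take n = 3 to 10 treated patients in an arm. One patient moved into or out of a table row changes that row's percentage by 100/n:

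- n = 3: 100/3 = 33.3 percentage points
- n = 5: 100/5 = 20.0 percentage points
- n = 10: 100/10 = 10.0 percentage points

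This further assumes that the patient has no other TEAE in the same row, since section 8.1 counts each patient once per preferred term.

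**The case against.** The strongest reply is that the intent is plain. The general rule, the first-day sentence's own default of counting the event, and the worst-case label all point the same way, and the literal reading defeats its own purpose. A competent programmer would probably do what was meant. This stands as an account of how the error arose: it is a wording slip and not a deliberate choice of analysis. It does not remove the conflict, because nothing elsewhere in the SAP corrects the sentence.

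Three stronger readings are tempting, and the document supports none of them.

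- *Every first-day event without a time will be misclassified.* That requires the first-day sentence to override the general rule and to be programmed literally. The SAP establishes neither; it contradicts itself.
- *Every event imputed to the first treatment date is misclassified as well.* The sentence speaks of missing times on that day and does not mention imputed dates. Partial dates are directly covered by the general rule, and the imputation convention is itself described as worst-case. Such events may be affected; it cannot be said that they are.
- *Incidences will shift by 10 to 33 percentage points.* That range is only 100/n for assumed arm sizes and one suitably placed patient. It does not estimate the effect of this defect.

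The mitigating facts also stand. All analyses are descriptive (section 4.1), so no inference or error rate depends on the flag. All adverse events are listed whatever their status (section 8.1). The serious adverse event table and listing are not stated to be limited to TEAEs (section 8.3). No event would vanish from the report, although the treatment-emergent indicator in the listing would carry the same error as the tables.

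**Conclusion.** The point holds as an internal contradiction in an operative rule. As written, the first-day sentence is the complement of the general rule and the reverse of its own label. If followed literally, it drops events of undetermined timing from the TEAEs and admits events shown to be pre-dose.

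The conclusion rests only on the wording of section 8.1. The reach to imputed dates is conditional on how the rules are chained. The number of affected events is unknown and could be zero. With a descriptive analysis and a full listing the practical impact is limited, but the sentence should be corrected because the main safety tables depend on the flag it defines.

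**What to change.** In the section 8.1 sentence on partial or missing times on the day of first treatment, change 'cannot' to 'can' in the exception clause. The event is then a TEAE unless it can definitely be shown to lie outside the treatment-emergent period, which matches the general rule. Check the TEAE flag program against the corrected sentence, including what it does with records whose date was imputed to the first treatment date.

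The cost is one word of SAP text and one program check. No new data are needed.
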